3.5.2 Frameworks to guide the development and optimization of an iKMC implementation model

We will use the concepts of the *Generic Implementation Framework* ²⁹ for the proposed study. This framework considers the non-linear and recursive nature of the implementation process as being foremost to implementation. At the centre of the framework is the innovation to be implemented, and surrounding the innovation are the contextual domains or levels of influence. Throughout the implementation process, we will consider factors, strategies, and outcomes that will influence the course of implementation. We strongly believe that adapting implementation based on process learning and the concurrent evaluation of coverage and quality is critical to achieving the optimal models, as demonstrated in the scale up KMC study.²⁹

Specifically, we will use the *Consolidated Framework for Implementation Research* in the Generic Implementation Framework ²⁹ to guide the development and process learning activities and include key concepts from the Dynamic Adaptation Process in implementation. ²³ The Consolidated Framework for Implementation Research is composed of the following five domains, with multiple constructs related to each domain:

- 1. Characteristics of individuals involved: This domain refers to characteristics of the individuals who would be key for implementation of the intervention, which include preterm or LBW newborns, mothers, parents and families, CHWs, midwives, nurse and doctors, facility managers, and programme managers at district, provincial and national levels. The study population are described in Section 3.4 above. The relevant constructs related to this domain include knowledge and beliefs about the intervention, self-efficacy, and individuals' motivation for change. These will all be explored during the formative research, and appropriate elements will be added to the implementation model. Finally, we will identify care-seeking practices for childbirth care including use of the private sector to determine how to strengthen care seeking and important stakeholders
- 2. Intervention definition and characteristics: This domain refers to characteristics of the intervention, which in this case will be iKMC. The intervention is described in detail in section 2.5 The specific barriers and facilitators to the implementation of the core elements of the intervention will be identified during formative research and the implementation model will be designed and adapted accordingly.
- 3. Outer setting or broader context: This domain refers to the economic, political, social, and cultural context which would influence implementation of iKMC. The relevant constructs related to this domain include resources for the care of preterm or LBW babies, relevant policies, political support, barriers, and enablers for efforts for newborn survival and KMC, societal norms and perceptions about care of the small infants and KMC. During formative research, we will review national, subnational and facility policies and standards to understand what policy changes need to be introduced to ensure implementation of iKMC. The cultural context that influences IKMC will also be explored
- 4. Inner setting or health system context: This domain refers to the health system, and health facility, and the context which would influence implementation of iKMC, including setting up M-SNCUs. The relevant constructs related to this domain include structural characteristics of the facilities, human resources and organization of care for preterm or LBW newborns, culture (overarching thinking about care of the small infants), implementation climate (need for change, compatibility with the intervention, relative priority, incentives, goals and feedback and learning climate), and readiness for implementation (leadership engagement, available resources, and access to information, knowledge and skills for implementing iKMC).

5. **Process of implementation:** This domain of the framework focuses on engaging the relevant stakeholders, executing, reflecting, and evaluating with the aim of optimizing the implementation model for iKMC. The process is described in detail in the sections below

3.5.3 Formative research

The first step in the study will be for the formative research team/ programme learning team to undertake an initial round of formative research to identify and understand barriers and enablers to implement iKMC in the specific local context. The overall aim of the formative research is to inform a user-centric design of the intervention model, based on the needs, motivations and influencers of the mother-infant dyad and a clear understanding of supply issues (through the health system and health workers) (linked to the domains in the Consolidated Framework for Implementation Research namely the characteristics of individuals involved, the outer setting or broader context and the inner setting or health system context). We will use mixed-methods to understand how KMC and iKMC is currently implemented in the study sites, including in the private sector, and context-specific factors affecting implementation. We will capture how preterm or LBW babies are currently cared for, barriers and facilitators to implementation, and context-specific factors that will affect implementation of iKMC in each site, including the perspectives on care of preterm or LBW babies of key stakeholders. The formative research phase will directly inform the development of an optimal iKMC implementation model in participating sites.

The specific objectives of the formative research phase are:

- To understand perceptions of women from varied backgrounds around care for preterm or LBW babies including care seeking practices and barriers and facilitators to reaching facilities, their perspective of care received in the health facilities, their perspectives on skin-to-skin care and breastfeeding, their concerns about caring for their baby and support they needed as well as acceptability of the intervention;
- 2. To explore family and community norms around support for care for preterm or LBW babies, community perceptions and values about care for preterm and LBW babies and KMC, and how to build family and community support for facility birth, referral to iKMC facilities and care for preterm or LBW babies in general and for iKMC implementation.
- 3. To explore health workers knowledge, norms and skills around care for the preterm or LBW babies and their perceptions about the feasibility and acceptability of different components of the iKMC implementation model;
- 4. To identify and understand factors affecting implementation and scale-up of iKMC, including existing policies and standards, the current practices to care for preterm or LBW babies, and explore the feasibility and acceptability of different components of the iKMC implementation model
- 5. To identify and agree with stakeholders the implementation strategies to barriers and enablers to effective implementation of the iKMC implementation model.

We propose the following activities in the formative phase:

- 1) Qualitative in-depth interviews (IDIs) with women who had preterm birth or LBW babies who were cared for in a study facility in the last month;
- 2) Focus group discussions (FGDs) with women in the community including those who gave birth in the last 12 months in a study facility or at home and female family members;
- 3) FGDs with men in the community including partners of women those who gave birth in the last 12 months in a study facility or at home
- 4) Small group (2-3 people) or individual interviews (depending on feasibility) with traditional birth attendants, women and community group leaders and other community stakeholders;
- 5) Small group (2-3 people) or individual interviews (depending on feasibility) health workers (CHWs, midwives, nurses, doctors, obstetricians, neonatologists, paediatricians and facility management);
- 6) Assessments of SNCUs to identify facility readiness for implementation of the WHO minimum package of care for small and sick newborn.

The qualitative study will take place in a sample of health facilities and community catchment areas across the six sites where iKMC interventions will be developed.

Additional details on the formative phase activities and programme learning, are included in Section 4 below. In addition, An assessment will be conducted of existing SNCUs to assess the facility's readiness to provide a basic, minimum level of care to preterm or LBW infants, including KMC. It will include an evaluation of the availability of 1) adequate infrastructure (e.g., closed thermoneutral space with handwashing facility, private

space for KMC), 2) human resources (number and type of staff, e.g., doctors and nurses trained in newborn care), 3) equipment and supplies (e.g., CPAP for respiratory support, pulse oximeters to ensure safe oxygen use), 4) standard operating procedures and protocols for newborn care (e.g., infection prevention and control including antibiotic administration, fluid management), 5) ability to support exclusive breastfeeding and assisted feeding for small newborns; and 6) detect and manage basic complications (e.g., hypoglycaemia and hypothermia).

3.5.4 Preparatory activities

The study team will conduct preparatory activities in selected districts, particularly in the selected hospitals where iKMC is to be implemented while formative research is being conducted. An important part of these preparatory activities will be to strengthen implementation of a minimum package of care for preterm or LBW babies requiring care in level 2 SNCUs (see Annex 1).

The iKMC trial identified two key common gaps in care: the provision of appropriate respiratory support and periodic clinical monitoring of babies.²³ These gaps will be covered by ensuring that adequate number of safe CPAP machines and pulse oximeters are made available at all iKMC implementing facilities. In addition, standard operating procedures for the use of this equipment will be developed and introduced. To ensure high quality and coverage of KMC for stable babies, learnings from the scale up KMC study will be implemented.⁴² The following activities will be done prior to the implementation of iKMC in level 2 M-SNCUs: (1) Activities aimed at maximizing access of preterm or LBW babies to iKMC-implementing facilities including accurate birth weight recording and referral of preterm or LBW babies born at home or lower-level facilities that do not provide KMC including skin-to-skin contact,

- (2) Activities aimed at initiating and maintaining KMC for stable preterm or LBW babies who were born in or referred to the facility in level 2 NICU through changes in infrastructure and training, motivation and support of facility staff. The level-2 NICU will be strengthened to provide effective interventions in the standard of care, including optimal use of CPAP, breastmilk feeding, prevention and treatment of infections, and monitoring,
- (3) Activities aimed to promote birth at a health facility. In case of a home birth, CHWs will identify a preterm or LBW baby and promote immediate care seeking at iKMC implementing facility. Activities will be undertaken to strengthen referral and transport. Community level activities will also support continuation of KMC at home after discharge; these include telephone contact by hospital staff with CHWs and families and home visits by trained CHWs. This network of primary, secondary level facilities and community will transform the small and sick newborn care in the study implementation area.

3.5.5 Development of the initial iKMC implementation model

Based on findings of the formative research, an initial model (Model 0+ in figure 8 below) for implementation of iKMC will be developed for implementation within the existing health system. This will be done in codesign workshops which will be held in each country under the leadership of national/provincial ministry of health, attended by the research group, district and hospital managers, doctor, nurse, and midwife leaders in participating hospitals, CHWs and women's and parents' groups representatives, and the WHO technical support team. We will facilitate group discussions to inform the implementation strategy using the APEASE criteria (Affordability, Practicability, Effectiveness, Acceptability, Safety, and Equity).²⁰ Similar methodology will be used during subsequent re-design workshops (see below).

Implementation Model 0+ will be initiated with concurrent programme learning as well as quantitative data collection on coverage and quality outcomes. The quantitative coverage and quality data will be the parameter for optimization of the implementation model, while the qualitative programme learning data (through interactions with managers, health workers, CHWs and women and families to understand their perspective on implementation) will provide answers to why we are achieving or not achieving the desired outcomes.

As mentioned above, the implementors will be routine health system staff, and they will be supported by a small implementation support team. The two other teams, a programme learning team and an outcome measurement team, will respectively collect the above-mentioned qualitative and quantitative data. The programme learning team will frequently share data with the implementation and implementation support teams to continuously improve implementation.

After implementation of the initial model for 3-6 months, a re-design workshop led by the Ministry of Health will be organized. At this meeting, lessons from implementation and data from programme learning and

coverage and quality measurement will be used to review and refine the implementation model. The aim of the re-design workshop would be to refine, improve and revise the implementation model to move towards a higher coverage of iKMC. A period of 3-6 months provides adequate volume and range of implementation experience with qualitative and quantitative data to support decisions on changes of the implementation model. However, this period will vary among the sites based on contextual needs.

The above process will be repeated every 3-6 months. We envisage at least three cycles during model design and optimization, until reaching a scalable model aiming for high coverage (aspirational for 80% coverage) and quality of iKMC. The WHO team will facilitate the sharing of learnings across different study sites to identify further opportunities to improve the implementation models. Experience from scale up of interventions such as KMC suggests that the development of the final (optimized) model may take about 12-18 months. Figure 8 summarizes this process of implementation model development and optimization.

Current government policy **Existing implementation** strategy (Model 0), usually based on expert consensu Formative research Program learning Ongoing qualitative data collection Government-led redesign Model 0+ developed at Model 1 workshop government-led co-design Developed and Considering implementation workshop, and implemented implemented (for 3-6 months) for 3-6 months) Evaluation Concurrent coverage and quality data collection Implementation support Iterative model optimization Problems identified and Process repeated until high solutions found on ongoing basis Optimized (scalable)

Figure 8 - Process of implementation model development and optimization

Source: reference 25

While the implementation model will largely focus on the hospitals where iKMC will be implemented, additional activities will be conducted in lower-level health facilities and communities in the study districts. A few examples of these activities are summarized in figure 9 below.

Figure 9. Activities expected in iKMC implementing facilities and communities in model optimization phase

Immediate KMC implementing facility

- Infrastructure changes to establish M-SNCU
- Strengthening the quality of care by implementing WHO minimum package of care for preterm and LBW babies
- Policy changes required for mothers and surrogates to be in level 2 M-SNCU 24/7 with the baby
- Arrangements in birthing room and operation theatres for immediate KMC and transport to level 2 M-SNCU in skin to skin contact
- Establish mechanisms for care of the mother in level 2 M-SNCU
- Training and mentoring of doctors (obstetricians & pediatricians), nurses and midwives for iKMC implementation Strengthening KMC for LBW and/or preterm babies who do not need -SNCU admission (KMC ward of the iKMC implementation facility)
- -Follow up care post discharge, linking with lower level facilities & CHWs

Primary care facilities

- Training and skill enhancement of facility staff in screening for referral cases & in WHO minimum package of care for preterm and LBW babies with KMC for babies not requiring referral.
- Identification of pregnant women who are likely to give birth to a preterm or LBW baby and their referral to an immediate KMC implementing facility
- Accurate birth weights and referral of LBW infants requiring care in skin to skin contact with mother or surrogate to iKMC implementing facility
- -Strengthen essential new born care and KMC implementation in PHC, CHC for babies not requiring referral (NCC, NBSU)

- Promote birth at a health facility
- In case a home birth, identify a preterm or LBW baby and promote immediate care seeking at iKMC implementing facility

Community-based activities

- Community actions to support transport of mothers and newborns to appropriate health facilities and to support care of preterm and LBW baby
- Training and skill enhancement of CHWs in postnatal care and KMC to support KMC practice at home post discharge or identify and initiate KMC for newborns not requiring referral

3.5.6. Identification of questions related to scalability of the implementation

Prior to initiation of the scale up of the model and stepped-wedge evaluation, the research team will engage with the administration, government, and programme managers at national and subnational level to identify the questions of scalability of the model within the existing system. These questions could be related to the scale up pathway and approach, potential barriers, capacity required for scale up, and investments needed. Addressing these questions throughout the duration of the evaluation will help prepare for provincial and national scale up, which will include development of the scale up strategy, investment case and implementation roadmap.

3.5.7 Recap of the study strategy in the model optimization phase

The first step will be the engagement of key stakeholders in the selected study districts, as described in the sections above. Two concurrent activities will be conducted in the first 2-4 months of the project implementation: formative research and strengthening the quality of care by ensuring implementation of the WHO minimum package of care for the small and sick newborn.²⁸

The formative research team will conduct interviews and focus group discussions to explore the domains of the consolidated framework for implementation research as described above. The duration of formative research will be relatively short, as this team will transition into the programme learning team and continue to collect relevant data throughout the model development and optimization period.

A rapid assessment of newborn care provided in the birthing room, operation theatre and level 2 NICU will also be conducted to identify gaps in implementation of the WHO minimum package of care for small and sick newborns. Based on the gaps identified, the study will support activities to address these gaps. When the results of formative research are available, co-design workshops to develop the implementation model 0+ will be organized. This model will be implemented, with ongoing collection of qualitative and quantitative data for 3-6 months, and re-design workshops will revise the model as required. Two or three similar iterative cycles will continue to optimize the implementation model until the end of the model optimization stage.

3.6 Outcome evaluation in the model optimization phase

3.6.1 Study population for outcome evaluation

The study population for outcome evaluation is common across both phases of the study.

Inclusion criteria

Preterm or LBW newborns (gestational age <37 weeks or birthweight<2.5 kg) requiring care in the SNCU, i.e., who are below the country cut-off point for birthweight or gestational age for SNCU admission, or those preterm or LBW newborns who are above the cut-off but are sick and need SNCU admission.

Exclusion criteria*

Preterm or LBW newborns requiring SNCU care who are critically sick, for example:

are unable to breathe spontaneously within the first hour after birth or

have congenital malformations that interfere with the intervention, or the intervention interferes with the required care for the congenital malformation (e.g., anencephaly, congenital heart disease, gastroschisis, hydrocephaly, multiple malformations, omphalocele, tracheoesophageal fistula, abdominal detention. etc.)

- are in shock (in need of inotropes) or are receiving invasive mechanical ventilation in the first 2 hours of birth or admission to SNCU; or
- Liveborn who died in the first 2 hours of birth or first 2 hours of admission or were dead at the time of admission to the iKMC implementing facility

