3.6.2 Outcomes for the model optimization phase

The main outcome of the design and optimization phase will be development of *the optimized implementation models* that achieves a high coverage and quality of iKMC and establish the norm of zero separation between the mother and her newborn in the four participating countries.

This will be measured through a primary coverage outcome in a tracer indicator that captures the skin-to-skin component of iKMC i.e., initiation and duration of skin-to-skin contact.

Primary coverage outcome: Proportion of preterm or LBW newborns requiring care in level 2 M-SNCUs) born in or brought to the iKMC implementing facility, within 24 hours of birth, who received iKMC. This will be captured through a tracer indicator on initiation and duration of skin-to-skin contact.

A baby is considered to have received iKMC if:

- Skin-to-skin contact is initiated within 2 hours after birth if the baby is born within the iKMC implementing facility, or within 2 hours of reaching the iKMC implementing facility if the baby is born outside the iKMC implementing facility (who reach the facility within 24 hours of birth) and
- Continuous skin-to-skin contact is provided by a mother/surrogate for at least 8 hours per day during the stay in the level 2 M-SNCU hospital (average hours per day for the overall M-SNCU stay)

Quality outcomes:

Proportion of preterm or LBW infants who arrived to an iKMC implementing facility within 24
hours after birth among those born in a health facility who required referred at birth to an iKMC
implementing facility

^{*}These neonates (except deceased newborns) will be excluded from the study for outcome measurement purposes however all newborns will receive appropriate care in the iKMC implementing facility.

- Proportion of preterm or LBW infants on respiratory support (any oxygen or CPAP) who received skin-to-skin contact > 8 hours/day in the M-SNCU
- Proportion of preterm or LBW infants receiving KMC at discharge (8-24 hours of skin-to-skin contact and exclusively breastfed) in the 24 hours before discharge from the iKMC implementing facility
- Proportion of preterm or LBW infants who are exclusively breastfed at discharge
- Median age at putting the baby to the breast for the first-time during M-SNCU stay

Implementation outcomes:

In the model optimization phase, we will also monitor the following implementation outcomes, including experience of care by mothers/caregivers and newborns:

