3.7.4. Trial facilities and trial participants

The trial facilities will be facilities having a functional level 2 SNCU. There should be at least one such facility in each of the study clusters. The trial participants will be preterm or LBW infants requiring care in the SNCU of the trial facilities, either born alive or brought alive to the trial facilities within 24 hours of birth, as per the inclusion and exclusion criteria in section 3.6.1. While the study will promote and strengthen immediate KMC for all preterm or LBW infants, the study population will only comprise preterm or LBW infants who require SNCU admission after birth as depicted in Figure 6.

Intervention

The intervention would be the optimized iKMC implementation model in each site. Core component of the intervention is the conversion of level 2 SNCU to level 2 M-SNCU in trial facilities during the intervention period. Preterm or LBW infants who require SNCU admission after birth, as depicted in Figure 6, will be admitted to M-SNCU where mother/surrogate will stay with the newborn on 24x7 basis and supported to provide KMC.

Control

Usual care (minimum package of care for small and sick newborns including KMC) will be provided to preterm or LBW babies during the control period. Preterm or LBW infants requiring SNCU care will be admitted to the SNCU.

Both groups: In both intervention and control period, most preterm or LBW infants will go to the postnatal or KMC wards after discharge from the SNCU/M-SNCU and will continue KMC until discharge from the trial facilities.

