3.7.6 Measurement strategy

The independent outcome evaluation team will collect data on impact, coverage, and process outcomes:

- Identification of preterm or LBW infants requiring SNCU care. The evaluation team will collect data
 on all preterm or LBW infants admitted to the SNCUs in the study area (all inborn and outborns brought
 in the first 24 hours after birth). They will also record the date and time of birth as well as the date and
 time of admission to the SNCU.
- Ascertainment of vital status: The evaluation team will collect the data on the vital status of all preterm or LBW infants admitted to the SNCUs in trial facilities (i.e., all inborn and outborns brought in the first 24 hours after birth) till discharge and day 28 after birth. This will be done by daily visits to all SNCUs in the trial facilities in pre-discharge period and through telephonic contact on day 28 after birth. The evaluation team will make a home visit if the infant/family cannot be reached on the telephone. The cause of death will be recorded using a standard WHO death certificate for all in-hospital newborn deaths.
- Ascertainment of secondary outcomes. We will strengthen the existing clinical record keeping in the SNCUs and the use of a separate SNCU register wherein the routine SNCU staff will record the key secondary outcomes like breastfeeding, clinical sepsis, hypothermia, and hypoglycaemia. During the daily visits, the study evaluation team will cross-verify the entries in the SNCU register using the clinical records and healthcare provider and/or maternal interviews. The optimal strategy will be worked out during the preparatory phase. Documentation of iKMC will be the same as in the model optimization phase.

The coverage and process outcomes will be measured as described in section 3.6.2. The measurement strategy for the secondary outcomes will be refined based on the learnings from the model optimization phase of the study.

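### The malformation exclusion rests on an untimed, open-ended judgement tied to an intervention given only after crossover, so infants could leave the mortality outcome at different rates by exposure

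*Protocol*

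**What the plan says.** Section 3.6.1 sets one study population for both phases. Its exclusions open with "Preterm or LBW newborns requiring SNCU care who are critically sick, for example", so the header itself is illustrative. The malformation item excludes infants who "have congenital malformations that interfere with the intervention, or the intervention interferes with the required care for the congenital malformation". Its list of examples ends with "multiple malformations, omphalocele, tracheoesophageal fistula, abdominal detention. etc".

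The other items are tied to a moment: infants who "are unable to breathe spontaneously within the first hour after birth"; infants in shock or "receiving invasive mechanical ventilation in the first 2 hours of birth or admission to SNCU"; and early deaths, tied to the first 2 hours of birth or admission or to being dead at admission.

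The footnote to these criteria, printed within section 3.6.2, says that the infants "will be excluded from the study for outcome measurement purposes however all newborns will receive appropriate care". A parenthesis just before these words exempts deceased newborns. Section 3.7.4 selects trial participants "as per the inclusion and exclusion criteria in section 3.6.1", and section 3.7.5 defines the primary outcome, death in the first 28 days, among trial participants. Section 3.7.4 also defines the intervention as the optimised iKMC model. Control infants receive usual care, which includes KMC.

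Section 4.1.2 has physicians at the facility identify eligible infants. Under section 3.7.6 the independent evaluation team will "collect the data on the vital status of all preterm or LBW infants admitted to the SNCUs in trial facilities". Table 4 (section 4.2.3) labels the primary outcome as among trial participants, but its denominator is all admitted infants and mentions no exclusions.

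**The concern.** Who counts in the primary mortality outcome should not depend on the exposure. Here three features leave room for that.

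- **Exposure-linked test.** Whether a malformation and iKMC get in each other's way is a practical question in an intervention period and a hypothetical one in a control period. The protocol does not say how to judge it in the latter.
- **No window.** The other criteria close at 1 or 2 hours, or at admission. This one does not, although a condition such as congenital heart disease may be recognised later than an abdominal wall defect.
- **Open list.** The examples leave the set of qualifying conditions to local judgement, and those judging cannot be blind once a unit has become an M-SNCU.

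Crossover also brings training, supervision and a push for earlier identification of eligible infants (section 3.7.2), so recognition could change at exactly that point. Malformed infants are likely to have high mortality. If more of them are excluded after crossover, counted mortality falls without any effect of iKMC. The model in section 3.7.7 adjusts for clustering and calendar time, but a shift that coincides with each cluster's own crossover cannot be separated from the treatment effect.

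**Working it through.** **Inputs from the protocol.** Control mortality 15% and target 12%, a 20% relative reduction or 3 percentage points; 92% power at the 5% level (section 3.7.7). The protocol gives no prevalence, mortality or recognition rate for malformations, so it has no figure of its own to reproduce on this point.

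**Assumptions (not in the protocol).** Malformed share of admissions M = 2–4%; their 28-day mortality d = 40–50%; overall mortality before this exclusion 15%; no true effect; the share e of malformed infants recognised and excluded rises from 1/3 to 2/3 at crossover and does not depend on whether the infant dies.

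**Formula.** Excluding a share e removes M·d·e deaths and M·e infants:

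counted mortality = (0.15 − M·d·e) / (1 − M·e)

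**Central case, M = 0.03, d = 0.40.**
- Control, e = 1/3: (0.15 − 0.004) / (1 − 0.01) = 0.146 / 0.99 = 14.75%
- Intervention, e = 2/3: (0.15 − 0.008) / (1 − 0.02) = 0.142 / 0.98 = 14.49%
- Relative risk 14.49 / 14.75 = 0.983; difference 0.26 points

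**Range.**

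| M | d | Control | Intervention | RR |
|---|---|---|---|---|
| 0.02 | 0.40 | 14.83% | 14.66% | 0.989 |
| 0.03 | 0.40 | 14.75% | 14.49% | 0.983 |
| 0.04 | 0.50 | 14.53% | 14.04% | 0.967 |

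The spurious relative reduction is about 1–3%. It is close to M·(d − 0.15)·(change in e) / 0.15. In the central case that is 0.03 × 0.25 × 0.333 / 0.15 = 1.7%, so half the gap in recognition gives about half the bias.

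**Direction.** With the same e in both exposures the two expressions are identical and RR = 1. With the two shares swapped, the central RR is 1 / 0.983 = 1.018, a spurious harm.

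**Effect on the test.** If the 5% level is two-sided, 92% power for 3 points implies a standard error of 3 / (1.960 + 1.405) = 0.89 points. A recalculation from the protocol's own inputs (24 clusters in 3 sequences, 125 infants per quarter, ICC 0.01, cluster autocorrelation 0.9, size variation 0.75), leaving the transition quarters unmeasured as in Figure 10, gives about 1.08 points. With no true effect, a shift of 0.26 points raises the 5% error to about 6.0% with the first value and 5.7% with the second. Over the table's range (0.17 to 0.49 points) it is 5.4–8.5% and 5.3–7.4%.

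**The case against.** The strongest case on the other side has five parts.

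- **One rule covers both exposures.** Any eligibility rule framed around an intervention is hypothetical for controls. Control care includes KMC, so control staff can judge compatibility with skin-to-skin contact. Several listed conditions, such as anencephaly, gastroschisis and omphalocele, are diagnoses that can be applied alike. This stands in part: it makes equal application possible, but the protocol does not require it.
- **Eligibility is probably meant to be settled at entry.** Section 4.1.2 identifies infants at birth or presentation, and Table 5 seeks consent on admission. This also stands. A reader might infer that infants can be dropped once a malformation is found at death, while undiagnosed survivors stay in. The protocol does not support that: no section describes removal after enrolment, and the footnote's parenthesis on deceased newborns could even mean that deaths are kept. No figure is therefore given for exclusion driven by death.
- **The abdominal item is unclear.** A reader might take it as distension acquired during the stay, and so as something iKMC could prevent. It stands in a list of congenital malformations, which does not cover acquired distension. The term needs correcting but does not carry that argument.
- **The size is assumed, small and of uncertain sign.** This is correct.
- **Much of the remedy is available.** Vital status is collected on all admitted infants, and a sensitivity analysis may already be in the analysis plan, which is not at hand. The eligibility rule, however, is fixed in the protocol, and it is the rule that is loose.

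**Conclusion.** The point holds as a weakness in a stated rule. Entry to the primary outcome depends on an exposure-linked, untimed and open-ended judgement by staff who know the exposure, and the planned adjustment would not remove a difference that arises at crossover. The protocol shows that differential exclusion is possible. It does not show that it will occur or in which direction.

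Under the assumed inputs the bias is about 1–3% in relative risk, small beside the planned 20%. It is nil with equal application and opposite in sign if control periods exclude more. The case for acting is that the rule governs a mortality outcome and is cheap to tighten before recruitment. The size of the likely bias would not justify it alone.

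**What to change.** **In section 3.6.1.** Replace the interference test with a closed list of named malformations recognised at birth or within the first 2 hours of birth or admission, the window already used for shock and ventilation. Remove the illustrative wording from the header and the list. Have the evaluation team apply the list from the birth or admission record in the same way in both exposures. State that infants whose malformation is recognised later stay in numerator and denominator. Correct or define the unclear abdominal term, and say which item the footnote's exemption of deceased newborns refers to.

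**In sections 3.7.5 and 4.2.3.** Reconcile the trial-participant population with the all-admitted denominator in Table 4.

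**In the analysis plan, if not already there.** Add a sensitivity analysis of 28-day mortality without the malformation exclusion, using the vital status collected under section 3.7.6, and report malformation exclusions by cluster and period.

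**Cost.** Wording changes and one case report form item (malformation and time of recognition). No extra infants or visits, and no change to care. Keeping malformed infants in dilutes the effect a little. In the central case, if all stayed in and none benefited while the true RR in the others was 0.80, intervention mortality would be 0.012 + 0.80 × 0.138 = 12.24% and the RR 12.24 / 15 = 0.816. The primary analysis would be diluted less, because only late-recognised infants stay in. Recognition within 2 hours may still differ somewhat by exposure; the sensitivity analysis addresses this because it does not depend on recognition.
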